9. URINE SAMPLE SHIPMENT & GLYPHOSATE ANALYSIS

9.1 Summary of Methods

Once all weekly and daily urine samples have been collected, analyzed, and stored for all 40 participants, two lab members will complete a quality assurance (QA) check of each cryovial to ensure that it is labeled with the correct barcoded label and that it is placed in the correct cryobox and correct cell, and that this information correlates with the information in the K01 Database, as well as with the Google Drive Cryobox Documents. The QA will be done thoroughly, but quickly, to prevent the thawing of the cryovials. Following the QA, the first of the four cryovials from every other week and the first composite cryovials from each week in the dietary intervention, along with a number of quality control vials and randomly selected cryovials, will be sent to the CDC for glyphosate analysis. These samples will be packaged by three lab members and then sent on dry ice to the CDC via Overnight Air Priority Shipping with tracking.

9.2 Materials

Quality Assurance

- Google Drive Cryobox Document
- K01 Database
- Nitrile gloves
- Frozen cryoboxes

Sample Shipment

- Twelve cryovial carrier boxes (labeled as box 1-12)

- Twenty-four small absorbent pads
- Twenty-four rubber bands
- Twelve biohazard bags
- Shipping cooler
- Shipping box
- Shipping stickers
- Shipping tape
- Nitrile gloves
- All weekly, composite, and daily cryoboxes in the -80°C freezer
- Four absorbent pads
- Five ice packs
- Five pounds of dry ice

9.3 Procedures

Quality Assurance

Weekly Urine Samples Electronic Documentation Check

The electronic database documents containing information on the stored weekly urine sample collections and cryovials will be exported from their original source. All changes to any of these documents will be done on the exported copies and will be tracked. No changes will be made the original data sources.

The lab member will cross-check the exported forms with the exported aliquot boxes document. The lab member will highlight any information on the

exported aliquot boxes document that does not match or that seems implausible. The lab member will briefly describe the issue in the margins of the exported aliquot boxes document. The lab member will refer to the Urine Chain of Custody Form as needed.

Weekly Urine Sample Cryovials Check

After completion of the Electronic Documentation Check, two lab members will cross-check the now highlighted exported aliquot boxes document with the frozen cryovials in order to 1) confirm that each cryovial is in the correct cell; 2) confirm that each cryovial is labeled correctly; and 3) clarify any typos or resolve other issues in the exported aliquot boxes document.

Documentation and Correction

After all the weekly cryoboxes have been checked and returned to the -80°C freezer, the lab members will review all the highlighting and notes in the exported aliquot boxes document. Typos will be corrected as appropriate.

Quality Assurance For Daily and Composite Urine Samples

QA for the daily and composite urine samples will follow the same procedures as QA for the weekly urine samples as described above.

Sample Shipment

Sample Selection

[name] will select 600 cryovials to send to the CDC. This selection will include the first of the four cryovials from every other weekly urine sample collected from each participant throughout the study. In addition, based on the weekly urine samples being sent to the CDC, [name] will randomly select participant IDs and week numbers to serve as weekly urine sample quality controls. For these urine samples the second of the four cryovials will also be sent to the CDC. [name] will also send the first of the two composite cryovials from each week of the dietary intervention from each participant to the CDC, as well as all 14 daily cryovials from one participant from each day of the dietary intervention to serve as composite sample quality control.

Supplies Preparation

Prior to the shipment of urine samples to the CDC, three lab members will set up a shipping station in the lab with the following supplies: 1) twelve cryovial carrier boxes; 2) twenty-four small absorbent pads; 3) twenty-four rubber bands; 4) twelve biohazard bags; 5) shipping cooler; 6) shipping box; 7) shipping tape; 8) shipping stickers; and 9) four absorbent pads. The lab members will also have five ice packs in the freezer and five pounds of dry ice in the -80°C freezer, and will have the Aliquot Boxes Spreadsheet available electronically.

Packaging and Shipping

Packaging will begin with weekly cryovials, then composite cryovials, and then daily cryovials. Cryoboxes will be pulled from the -80°C freezer one at a time and the selected cryovials from that cryobox will be transferred to a cryovial carrier box.

The lab members will place the five ice packs from the freezer at the bottom of the shipping cooler and place two absorbent pads on top. The lab members will then remove all twelve cryovial carrier boxes in biohazard bags from the -80°C freezer and place them into the shipping cooler along with five pounds of dry ice. Finally, two more absorbent pads will be placed on top and the lid to the shipping cooler will be taped closed with one single strip of shipping tape running horizontally across the lid. The shipping cooler will be placed into the shipping box and the shipping box will be taped closed with one single strip of shipping tape running horizontally across the box. No more tape should be used on the shipping cooler or shipping box as the dry ice in the shipment must not be completely sealed off from oxygen.

Appropriate shipping stickers will be placed on the shipping box, and the box will be transported for Overnight Air Priority Shipping with tracking with early morning arrival. The lab members will email the CDC to provide the tracking information, and will also request that the CDC confirm receipt of the samples and that all samples arrived frozen once the shipment arrives.

SAP  
Measurement of Agricultural and Dietary Glyphosate Exposure among Pregnant Women  
NCT04155463  
July 1, 2022

**Target journal:** Environmental Health Perspectives

**Study Design:** Randomized cross-over trial

**Research objective:** Examine differences in specific gravity-standardized urinary glyphosate levels between a one-week conventional diet and one-week organic diet among 40 pregnant women

**Hypothesis:** Urinary glyphosate levels will be significantly lower during the one week in participants consumed organic diets, compared to the one week in which they consumed their normal conventional diet. Reductions will be even greater among participants living > 0.5 km from agricultural fields.

**Statistical Analysis Plan:**

1. Calculate the average glyphosate concentration from the two sets of seven individual daily samples that were analyzed and confirm that the average is the same as the value from the composite sample for that participant
2. Calculate detection frequencies and examine normality of the data
3. Impute any values <LOD as  $\frac{LLLLL}{\sqrt{2}}$
4. Adjust urinary values for specific gravity, based on Chiu et al. 2018,  $C_{SG} = C * [(Avg_{SG} - 1) / (Ind_{SG} - 1)]$  where  $Avg_{SG}$  is the average specific gravity measured in the cohort as a whole and  $Ind_{SG}$  is the specific gravity of the individual sample being adjusted.
5. If the data are non-normally distributed, run two-tailed Wilcoxon sign rank test to assess difference in urinary glyphosate levels between the conventional and organic diet weeks. If the data are normally distributed, run two-tailed paired t-tests for this comparison.
  - a. Primary analysis:
    - i. All 39 individuals
  - b. Secondary analyses:
    - i. Exclude participants missing  $\geq 4$  samples from either week
    - ii. Exclude participants who didn't turn in food diaries
    - iii. Exclude participants who didn't write anything for food consumed from outside of study
    - iv. Exclude participants who had a Likert scale <22 (include imputing "0" for any "N/As" from each day)
    - v. Exclude participants who scored <36 on writing foods down
    - vi. Additional combinations of the above exclusions may be explored
  - c. Stratified analysis:
    - i. Evaluate the above comparison separately among those living  $\leq 0.5$  km from an agricultural field vs. > 0.5 km from an agricultural field

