1.5 Scope

Glyphosate is the most commonly used herbicide in the world. This increase has been driven, in large part, by the introduction of glyphosate-resistant crops such as “Roundup Ready” corn and soybeans. In Idaho, nearly a quarter million acres of Roundup Ready sugarbeets are cultivated each year.

Human exposure to glyphosate and its formulations may occur through dietary, agricultural and residential pathways. Despite its extensive use, frequent presence in foodstuffs and environmental media, and potential toxicity, current exposure levels in human populations are not well documented. However, several studies have suggested that in utero exposure to glyphosate and glyphosate formulations may have reproductive effects and adversely impact developing fetuses. This study therefore aims to quantify pathways of glyphosate exposure among pregnant women.

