6. DIETARY INTERVENTION

6.1 Summary of Methods

The dietary intervention will take place over the course of 17 days, from June 14 to June 30. Participants will receive one week of conventional groceries and one week of organic groceries, the order of which will be randomly assigned. Each week, each study participant will shop for up to \$150 worth of groceries using an online account at a local grocery store, and grocery orders will be delivered to participants. Participants will track their food intake each week using a Food Log. During the dietary intervention, participants will not provide weekly urine samples and will instead provide 14 daily urine samples.

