7. DAILY URINE SAMPLE COLLECTION

7.1 Summary of Methods

Daily urine samples will be provided during the dietary intervention during Week One, from June 16-22, and during Week Two, from June 24-30. Participants will provide a total of 14 daily urine samples. Daily urine samples will be numbered sequentially. Each day, each study participant will provide a first morning void sample and will place the sample in her cooler with her ice pack outside her home. A lab member will then collect that day's sample, provide the participant with a specimen cup for the following day, and bring that week's sample back to CAHL in a lab cooler with a lab ice pack. Once back at CAHL, the lab member will analyze and store the daily urine sample.

Daily urine sample collections will follow the same protocol as described in Section 4 of this document, with the following major deviations:

- Lab members will collect and deliver daily urine sample cups, rather than weekly urine sample cups
- Lab members will complete a Daily Urine Chain of Custody Form, rather than the Urine Chain of Custody Form.
- For non-local collections two days of daily urine samples will be collected during a two-day trip. On the first day a lab member will drive to that area, collect the daily urine samples for that day, transport the daily urine samples in a lab cooler with a lab ice pack to a hotel, and store the daily urine samples in the study refrigerator at the hotel. The lab member will spend the night at the hotel, and then on the second day the lab member will collect the daily urine samples for that day and bring the urine samples for both days back to CAHL in a lab cooler with a lab ice pack
- Participants will receive one \$50 gift card at the end of the dietary intervention period if they provided all 14 daily urine samples, rather than receiving a \$10 gift card for each sample collected

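### The primary paired test of this two-period cross-over has no period term: valid on average, but a change shared by all women between the two June weeks would cost power and, with unequal diet orders, shift the estimate

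*SAP*

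**What the plan says.** The SAP header gives the design as "Randomized cross-over trial". Protocol section 6.1 gives each woman one conventional and one organic week, "the order of which will be randomly assigned". It states no ratio or blocking, and neither document gives the number of women in each order. Sampling dates are common to everyone: protocol section 7.1 has daily samples during "Week One, from June 16-22, and during Week Two, from June 24-30".

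The primary comparison, in all 39 women, is SAP step 5: "run two-tailed Wilcoxon sign rank test to assess difference in urinary glyphosate levels between the conventional and organic diet weeks". The alternative is "If the data are normally distributed, run two-tailed paired t-tests for this comparison". Steps 5b and 5c repeat the same comparison after various exclusions and by distance from a field. Period and order are not mentioned at any step.

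**The concern.** Because the two weeks are the same dates for all women, anything that changes between them for everyone is mixed into the diet comparison. Women who ate organic second carry the change with one sign, and women who ate organic first carry it with the other. A paired test that ignores order treats this as noise and, when the orders are unequal in number, as part of the diet effect.

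A non-diet change is possible on the documents' own account. Protocol section 1.5 says: "Human exposure to glyphosate and its formulations may occur through dietary, agricultural and residential pathways". The SAP hypothesis adds: "Reductions will be even greater among participants living > 0.5 km from agricultural fields". That also means a change need not be the same for every woman.

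The issue affects the primary result and every subset that reuses the test. Without the order counts, a reader cannot judge whether a difference between the weeks could have moved the result.

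**Working it through.** The plan gives no power, effect size, SD or alpha, so there is no stated figure to reproduce.

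**Inputs from the documents:** N = 39 (SAP step 5a), randomised order (protocol 6.1), common sampling weeks (protocol 7.1), no period term (SAP step 5).

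**Assumed:** two-sided alpha 0.05, a 30% reduction on organic, SD of the within-woman log ratio 0.7, and a shared Week Two/Week One change of 1.1-, 1.25- or 1.5-fold in either direction.

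**Algebra.** Let D be organic minus conventional, τ the diet effect, π the shared Week Two minus Week One change, and s = +1 if organic is second, −1 if first. Then D = τ + sπ + e. With n1 women organic-second and n2 organic-first:

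- mean of D = τ + π(n1 − n2)/N, a displacement of 1/39 = 0.026π at 20/19 and 9/39 = 0.231π at 24/15;
- added variance of D = π²[1 − ((n1 − n2)/N)²]. At 20/19 and π = 0.5 SD the test's standard error grows by √(1 + 0.25 × 0.999) = 1.12, equivalent to about 39/1.25 = 31 women.

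The Week Two minus Week One difference has mean π + τ in organic-second women and π − τ in organic-first women. Half the between-order difference is therefore τ, free of π. Its standard error is (SD/2)√(1/n1 + 1/n2), against SD/√N for the paired mean when π = 0. The ratio is 1.00 at 20/19, 1.03 at 24/15 and 1.05 in a subset of 20 split 13/7.

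**Simulation, log scale, all values detected.** Ranges cover both tests and both directions.

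| Split, shared change | Type I error, planned | Type I error, adjusted | Power, adjusted minus planned |
|---|---|---|---|
| 20/19, 1.1-fold | near 0.05 | near 0.05 | within 1 point |
| 20/19, 1.25-fold | about 0.04 | near 0.05 | about 1 to 3 points |
| 20/19, 1.5-fold | 0.02–0.03 | 0.04–0.05 | 5 to 11 points |
| 24/15, 1.25-fold | about 0.06 | near 0.05 | depends on direction |
| 24/15, 1.5-fold | 0.076–0.078 | 0.04–0.05 | depends on direction |

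At 24/15 and 1.5-fold, planned power is 0.46–0.51 in one direction and about 0.95 in the other; adjusted power is 0.83–0.86 in both.

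At 20/19 and 1.5-fold, the power gain is 2 to 6 points with SD 0.5 and 3 to 9 with SD 1.0. It falls to 0 to 3 if only half the women have the change.

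**Untransformed values, as step 5 is written.** With 0, 20% or 40% non-detects imputed and then adjusted for specific gravity, the gain at 20/19 is −1.5 to +1.0 points at 1.1-fold, −0.8 to +3.2 at 1.25-fold and +1.9 to +9.4 at 1.5-fold. At 24/15 and 1.5-fold, planned type I error is 0.068–0.073 (signed-rank) or 0.054–0.058 (paired t).

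The displacement of the mean has a closed form. Take organic mean 0.7, conventional 1.0 and Week Two multiplied by f = 1.5. The target is −0.3 × 2.5/2 = −0.375. At 24/15 the planned mean is [24(1.05 − 1) + 15(0.7 − 1.5)]/39 = −0.277, which is 26% too small; reversing the split makes it 26% too large. At 1.25-fold the error is 15%. At 20/19 the errors are 3% and 2%.

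**Chance of imbalance.** Under simple 1:1 randomisation of 39, a split of 24/15 or worse has probability 0.20; under blocking it is less likely. Averaged over simple randomisation (log scale), planned type I error is 0.048–0.050. Signed-rank against rank-sum power is 0.855 and 0.839 with no change, 0.822 and 0.842 at 1.25-fold, and 0.738 and 0.841 at 1.5-fold.

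**Cost when there is no change.** At 20/19, none for the t-test and 1 to 2 points for the rank-sum; at 24/15, 2 to 4 points; at 13/7, 3 to 6 points (log scale: 0.558 falls to 0.495 for rank tests, 0.580 to 0.538 for t-tests).

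**The case against.** Randomising the order already protects the planned test: averaged over randomisation its type I error is correct, and near balance it is conservative. On this view the choice is about efficiency. The sampling weeks are only eight days apart from midpoint to midpoint, each weekly value is a seven-day composite, and recruitment spans several health districts, so an equal simultaneous change in all women is not the default expectation. The striking type I errors need both a 1.5-fold change and a 24/15 split. Adjustment can cost power in small unbalanced subsets and, on untransformed values, gains little or nothing at small changes. Replacing the primary test after the laboratory results are known would be a post hoc change.

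Much of this stands. The test is valid on average, provided each order had probability one half, which the protocol does not state. The likely loss at 20/19 with a modest change is small. The cost in subsets is real, and for that reason the planned test should stay beside the adjusted one there. The timing point also stands: SAP step 1 refers to "two sets of seven individual daily samples that were analyzed", in the past tense, so results may already have been in hand.

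None of this removes the case for analysing by the randomised order. The trial has one realised split, not an average over splits. The exclusions and the distance strata do not preserve balance. Near balance in the full set, adjustment costs almost nothing.

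**Conclusion.** The concern holds. The missing period term and the algebra are certain. The size of the effect in this trial is unknown, because neither the change between the weeks nor the order counts are given. Near 20/19 the consequence is a conservative test with less power: negligible at 1.1-fold, about 1 to 3 points at 1.25-fold and 5 to 11 at 1.5-fold on the log scale. With clearly unequal orders the estimate and the conditional type I error move as well. These figures rest on the assumed SD, effect and change. On untransformed values, adjustment does not fully remove a multiplicative change: adjusted rank-sum power is 0.77 with no change and 0.74–0.75 at 1.5-fold. The amendment should be made because it is cheap; the planned analysis is not invalid.

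**What to change.** - Report the number of women in each diet order, overall and in each exclusion subset and distance stratum.
- For all 39, compare Week Two minus Week One differences between the two randomised orders, by two-sample t-test, or by rank-sum if those differences are non-normal. Give half the between-order difference as the diet effect with a 95% CI (half the Hodges-Lehmann shift for the rank-sum). Report the planned paired test alongside it.
- If outcome data had been seen before this change, label the period-adjusted result as added and show both.
- In subsets, place the period-adjusted result next to the planned test, not in place of it. Do not rely on the rank-sum where one order is very small. Its smallest two-sided p is 2/C(n1 + n2, n1): 0.071 at 6/2, 0.044 at 8/2, 0.057 at 4/3 and 0.036 at 5/3. About five women per order is a workable minimum; below that, give the estimate descriptively.

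The cost is SAP wording and a few lines of code. The planned test already needs to know which week was organic for each woman, and her personalised flyer (protocol 6.4) records it. The power cost is as given above. This change does not address carry-over.

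### The SAP's second hypothesis, a larger reduction beyond 0.5 km from fields, has no planned test: step 5c.i tests each distance group separately and never compares them

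*SAP*

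**What the plan says.** The Hypothesis paragraph of the SAP makes two claims. The first is that urinary glyphosate is lower in the organic week. The second concerns distance from fields: "Reductions will be even greater among participants living > 0.5 km from agricultural fields".

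Step 5 of the Statistical Analysis Plan defines the comparison and its two possible tests. For non-normal data the plan is to "run two-tailed Wilcoxon sign rank test to assess difference in urinary glyphosate levels between the conventional and organic diet weeks". Otherwise: "If the data are normally distributed, run two-tailed paired t-tests for this comparison". Both are paired tests within each woman. The primary analysis, step 5a.i, covers "All 39 individuals".

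Distance enters once, in step 5c.i: "Evaluate the above comparison separately among those living" at or within 0.5 km of an agricultural field and those farther away. The comparison it refers back to is the diet-week test of step 5.

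The SAP contains no interaction term, no two-sample or rank-sum test of the individual reductions, and no interval for a difference between the distance groups. The protocol is a set of operating procedures without a statistical section, so it does not fill the gap.

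**The concern.** The second hypothesis is about a difference between two groups of women. A paired test inside one group asks whether that group's reduction is zero. Two such tests do not ask whether the two reductions differ. A significant result in one group beside a non-significant result in the other can arise from unequal group sizes or from chance, with identical true reductions.

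The SAP also does not say whether a greater reduction means more in absolute concentration or more in proportion. If the groups start from different conventional-diet levels, the two scales can rank them differently.

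At stake is the distance claim. The most likely informal reading would be that the far group is significant and the near group is not. That pattern could be reported as support when the data contain no evidence of a difference.

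**Working it through.** **What can be reproduced.** The documents give no sample size calculation, alpha, SD, effect size or stratum sizes. The one usable figure is the 39 women of step 5a.i. Everything else below is assumed. Splits are written far/near.

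**1. Analytic check (t-tests, two-sided 5%, same standardised paired effect d in both groups).** Power in a group of n women comes from the noncentral t distribution with n − 1 degrees of freedom and noncentrality d√n. Women in the two groups are independent, so

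P(only far significant) = power(far) × [1 − power(near)].

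At d = 0.46 the test on all 39 women has 80% power. Then:

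| Far/near | Power far | Power near | P(only far significant) |
|---|---|---|---|
| 29/10 | 0.667 | 0.255 | 0.667 × 0.745 = 0.50 |
| 26/13 | 0.616 | 0.332 | 0.616 × 0.668 = 0.41 |
| 19/20 | 0.475 | 0.497 | 0.475 × 0.503 = 0.24 |
| 13/26 | 0.332 | 0.616 | 0.332 × 0.384 = 0.13 |

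Over d = 0.3 to 0.7 and these four splits, the range is about 4% to 52%.

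**2. Simulation with the signed-rank test, equal effects.** The log(organic/conventional) ratios are normal with SD 0.7, with 4,000 trials per setting. A group counts as significant if p < 0.05 in the direction of a reduction. The table shows the percentage of trials with only the far group significant, by true log ratio:

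| Far/near | 0 | −0.2 | −0.4 | −0.6 | −0.8 |
|---|---|---|---|---|---|
| 29/10 | 2 | 26 | 53 | 35 | 12 |
| 26/13 | 3 | 23 | 44 | 20 | 5 |
| 20/19 | 2 | 18 | 24 | 6 | 0.6 |
| 13/26 | 2 | 10 | 10 | 2 | 0 |
| 10/29 | 2 | 9 | 6 | 1 | 0 |

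A two-sided 5% rank-sum test of the log ratios between the groups errs in the far direction in about 2% to 3% of trials in every cell.

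Sensitivity at −0.4, for 29/10, 20/19 and 10/29:
- SD 0.5: 40%, 9%, 1%.
- SD 1.0: 43%, 24%, 9%.
- Untransformed differences with lognormal concentrations (between-woman log SD 0.8, assumed): 51%, 25%, 8%.

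**3. Simulation with the hypothesis true** (log ratio −0.6 far, −0.2 near, SD 0.7):

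| Outcome | 29/10 | 20/19 | 10/29 |
|---|---|---|---|
| Only far significant | about 87% | about 74% | about 47% |
| Both significant (no answer) | 12% | 20% | 20% |
| Only near significant (wrong way) | 0.2% | 1% | 10% |
| Direct rank-sum test significant | 31% | 38% | 29% |

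**4. What a direct comparison can deliver with 39 women.** A two-sample t-test on the within-woman differences has 80% power for a difference of 0.92 SD at a near-even split, 0.98 SD at 26/13 and 1.06 SD at 29/10. For a 0.5 SD difference its power is 33%, 30% and 26%. In the SD 0.7 setting, the mean 95% half-width on the log scale, from a pooled t interval, is 0.45 at 20/19 and 0.52 at 29/10 or 10/29. Back-transformed, the limits are the estimate divided and multiplied by e^0.45 = 1.57 or e^0.52 = 1.68.

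**The case against.** **The SAP is brief throughout.** It names tests only and specifies no estimate or interval even for the primary analysis. Nothing stops the authors from reporting the reduction in each group for readers to compare, and the SAP does not prescribe a comparison of p-values. This stands in part. The supportable claim is that no contrast between the groups is specified, not that every estimate is ruled out. Two group estimates without an interval for their difference still do not test the hypothesis.

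**Step 5c.i might mean that the groups are compared.** It sets one group against the other, but its verb asks for separate evaluation, and the only tests named are paired ones, which cannot compare different women. If a contrast was intended, its statistic and scale are still missing.

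**The size of the harm is not anchored.** This is correct. The range runs from negligible to more than half. The high values need a far-heavy split, and with near-heavy splits the figure stays near 10% or below. The documents do not say which split applies.

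**When the hypothesis is true, the informal reading often points the right way**, in about 87%, 74% and 47% of trials, whereas the direct test has 29% to 38% power. These figures belong beside the others. They do not rescue the informal reading, because the same pattern is also common when the effects are equal and so cannot discriminate.

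**Low power makes the added test often inconclusive.** This is true, and it is a reason to show an interval, since two p-values hide that imprecision.

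**Conclusion.** The concern holds on the text alone and depends on no simulated number. A stated hypothesis about a difference between groups has no matching analysis; followed exactly, the plan cannot answer it. It should be fixed, but it does not affect the primary diet comparison in step 5a.

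The numerical illustration rests on assumed splits of the 39 women, an assumed alpha of 5%, and assumed SDs and effects. On those assumptions, judging the hypothesis by which group is significant gives false support in about 0% to 53% of trials, highest when most women live far from fields and the effect is moderate. A direct test keeps this at about 2% to 3%. The authors know the actual split and can see where in the range they fall.

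**What to change.** Add one step to the SAP, labelled exploratory. Suggested text:

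> 5c.ii. For each woman, compute log(organic/conventional) from the specific-gravity-adjusted composite values. Compare women living more than 0.5 km from a field with the remaining women by a two-sided rank-sum test. Report the number of women in each group and the Hodges-Lehmann difference, back-transformed to a ratio of ratios, with its 95% confidence interval. Reduction here means relative reduction. The results of 5c.i are descriptive and are not used to judge the second hypothesis.

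If absolute reduction is meant, apply the same test to each woman's conventional-minus-organic difference. The rank-sum test is valid whichever branch of step 5 applies. A two-sample t-test under step 5's normality rule would follow the existing plan more closely. A diet-by-distance term in a log-scale mixed model is another option. These are not equivalent, so one should be chosen in advance.

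Timing matters. The SAP is dated July 1, 2022, already fixes the analysis at 39 women and refers to analysed daily samples. If results by distance have been seen, the comparison must be labelled post hoc.

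The cost is one step and one test on data already collected, plus a commitment to absolute or relative reduction. With power of about 30% to 40% in the case examined, a non-significant result must not be read as evidence that distance makes no difference.
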